8.2 Statistical Hypotheses

The primary objective of the study is assessment of safety. Therefore, there are no formal statistical hypotheses associated with any of the endpoints. Safety endpoints for SH and DKA will be compared to historical published data. Efficacy endpoints will be compared across study periods with the run-in period designated as the comparator study period. P-values for differences between study periods on both safety and efficacy endpoints will be calculated, however, will not be used for formal statistical inference due to the exploratory nature of the study objectives and the lack of correction for multiple testing.

8.3 Sample Size

comparing continuous outcomes.

The sample size of at least 30 adults and adolescents age 14+ years old, 30 children age 6-13 years old, and 12 preschool participants age 2-5 years of age who will complete the trial was selected to have a reasonable time period of use in each age cohort to establish safety, with each subject completing 2 weeks of Control-IQ 1.5 technology use, 2 weeks of Control-IQ 2.0 technology use with the target of 112.5 to 160 mg/dL, and 2 weeks of Control-IQ 2.0 technology use with the target of 90-130 mg/dL. The choice of sample size is not based on statistical principles. In addition, the sample size assures a reasonable number of late bolus meal challenges completed.

There is a further enrollment goal of at least half of all participants in each age group have an HbA1c at baseline of $\geq 7.5\%$, and have at least 6 participants age 14-17.

8.4 Outcome Measures

Primary Endpoints

- 1. Severe hypoglycemia (with cognitive impairment such that assistance of another individual is needed for treatment) during study compared with data on severe hypoglycemic events reported by T1D Exchange clinic registry over a 3-month time period
- 2. Diabetic ketoacidosis during study compared with data on DKA events
- 918 3. Number of unanticipated adverse device effects
- 919 4. Number of other serious device-related adverse events

920 Secondary Endpoints

1. All device-related adverse events

2. CGM hypoglycemia outcomes, compared between the three study time periods 922 a. Overall % time <54 mg/dL 923 b. Overall % time <70 mg/dL 924 3. Times in ranges-overall (70-180 mg/dL, >180 mg/dL, >250 mg/dL, 70-140 mg/dL) compared 925 between the three study time periods 926 4. Mean glucose compared between the three study time periods. 927 5. Overall variability (CV and SD) compared between the three study time periods 928 6. Secondary endpoints 2 - 5 compared during daytime and nighttime, across the three study time 929 930 periods 7. Secondary endpoints 2 - 5 as well as adverse events, during the study meal challenge periods, for 931 late bolus feature use compared to normal bolus in the meal challenges. 932 8. Time to intervention for hypo- or hyperglycemia during the study meal challenge periods, for late 933 bolus feature use compared to normal bolus in the meal challenges. 934 935 9. Number of interventions for hypo- or hyperglycemia during the study meal challenge periods for late bolus feature use compared to normal bolus in the meal challenges. 936 10. Subgroup Analysis for all metrics by age cohort, baseline HbA1c cohort (HbA1c at baseline of > 937 7.5%, yes/no), and target activity use (standard target, lower target, sleep activity, exercise 938 939 activity). 940 8.5 Analysis Datasets 941 942 Safety analysis set: All participants who initiate the Treatment Period and use the study device at least one time (including training). 943 CGM analysis set: Any member of the Safety Analysis Set who has at least 24 hours of CGM data during 944 945 either Treatment Period. CGM data occurring within the meal challenge windows (from time of start of meal up to 5 hours afterwards [3 hours for age 2-5]) will not be used to determine whether a subject is 946 included in CGM analysis set or not. 947 948 Late bolus meal challenge set: Any member of the Safety Analysis Set who has at least 24 hours of CGM data during the Treatment Period, and who has at least 3 hours of CGM data for at least one meal 949 challenge. 950 8.6 Analysis of Endpoints 951 8.6.1 Analysis of the Safety Event Endpoints 952 953

Safety events (not including CGM defined events defined in sections 6.2.2, 6.2.3, and 6.2.4) will be based on Safety analysis set, and tabulated for each primary endpoint as the number of events per participant, the number of participants with ≥ 1 event, and the rate of events per 100 person-years. A 95% confidence interval will be calculated for the rate of events per 100 person-years.

Since study eligibility excluded participants with 2 or more severe hypoglycemia or DKA events in the

Since study eligibility excluded participants with 2 or more severe hypoglycemia or DKA events in the prior 6 months, an unbiased comparison of the event rate during the Treatment Period with the pre-study event rate is not possible. Therefore, the severe hypoglycemia and DKA event rates will be compared with the T1D Exchange data, which reported the frequency of 1 or more severe hypoglycemia and DKA events in the prior 3 months. The proportion of participants with events during the Treatment Period (each

958

959

960

961

period separately) will be compared with the run-in period as well as with the T1D Exchange frequency.
Differences in proportions across the three study periods (two active treatments and the run in) will be estimated in a pairwise fashion, and statistical significance will be assessed using a normal approximation to a binomial distribution.

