3.3 Visit 6: Control-IQ 2.0 Training Visit

- After participants complete the run-in, they will return for the Control-IQ 2.0 training visit, and switch to
- the Control-IQ 2.0 study pump after training by qualified staff.
- Control-IQ 2.0 allow for selection of different glycemic targets, as well as toggling autoboluses in
- standard and exercise activity. The late bolus feature will also be available.
- Participants will be randomized to use either a daytime 30-min predictive glucose target of 90-130 mg/dL
- or 112.5 to 160 mg/dL for the first two-week period, then switch to the other target after 2 weeks.
- In the training visit, participants will:

327

328

329

332

337

345

346

347

348

349

350

351

352

353

354

355356

357

358

- 1) Select the appropriate target in clinic on their study pump per the randomization, and will be instructed by study staff to use the assigned glycemic target during each two week period.
 - 2) Be instructed that autoboluses will default to on during normal activity, and off during exercise activity.
 - 3) Be reminded again that use of the security PIN on the insulin pump will be required for anyone who is not entirely responsible for their own diabetes care, to include all 2-5 year olds, and those 6 years of age or older who may be only partially responsible for their own diabetes management.
 - 4) Be instructed that sleep activity will be required during Control-IQ 2.0 use. A sleep schedule should be programmed into the pump for use each night. Participants will be instructed to disable sleep or adjust the schedule on the nights of the late bolus meal challenges, then re-enable sleep activity as soon as the challenges are over, so it is used the rest of the night.
 - 5) Review prior training guidelines from the Control-IQ technology 1.5 training visit, and be taught how the new features are different in Control-IQ technology 2.0.
 - 6) Review the study meal late bolus challenges, to be performed twice in each two week period. Participants may also use late bolus as desired outside of the challenges.
- The participant will be given a User Guide as a reference as well as review the Hypoglycemia and
- Hyperglycemia Treatment Guidelines as part of the Study Participant Instruction Sheet. The study device
- training form will be completed.
- Participants will be instructed to download the study device prior to each phone contact or office visit.

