457 458	In addition, real-time CGM alerts will be sent to study staff providers (MD, DO, NP, PA) for all 2-5 year old participants throughout their use of Control-IQ 2.0 technology (all 4 weeks).

459	Chapter 4: Study Devices and Drugs
460	4.1 Study Devices
461	4.1.1 Insulin Pump
462 463 464	For the run in period, participants will use a study provided Tandem t:slim X2 with Control-IQ 1.5 technology (Investigational Device). For the treatment period, participants will use a study provided Tandem t:slim X2 with Control-IQ 2.0 technology (Investigational Device).
465	4.1.2 Continuous Glucose Monitoring
466 467	The study CGM is the commercial version of the Dexcom G6, which includes a transmitter and sensors. The CGM sensor will be replaced at least once every 10 days.
468	4.1.3 Blood Glucose Meter
469	The study blood glucose meter is the Contour® NEXT (Ascencia Diabetes Care).
470 471 472	Blood glucose levels will be measured using the study's blood glucose meter (glucometer) and the CGM device will be calibrated if needed using the study glucometer and strips in accordance with the manufacturer's labeling.
473	4.1.4 Ketone Meter
474 475	The study blood ketone meter is the Precision Xtra Blood Glucose and Ketone Monitoring System (Abbott Diabetes Care).
476 477	Blood ketone levels will be measured when needed to evaluate prolonged hyperglycemia. The blood glucose meter component of the Precision Xtra device will not be used.
478	4.2 Study Device and Drug Accountability Procedures
479 480	Device accountability and inventory will be documented to include detailed inventory records of the study CGM supplies, and Tandem insulin pump system.
481	4.3 Participant Access to Study Device at Study Closure
482 483 484	Participant will return all investigational study devices and supplies (insulin pump, CGM and related supplies) at study closure. Participant may keep the study ketone meter and study glucometer if these devices are not marked for investigational use only.

Chapter 5: Testing Procedures and Questionnaires

486	5.1 General Challenge Guidelines
487 488 489	All study participants will complete two late bolus meal challenges during each two week treatment period. Participants will be instructed to wait at least 48 hours after switching targets in the treatment period to perform the next set of challenges.
490	A minimum of 48 hours will occur between all challenges for each participant.

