8.6.2 Analysis of Other Safety Endpoints

966

976

990

995

1003 1004

Safety summaries will be based on Safety analysis set. All adverse events reported over the course of the study will be summarized by study period for run-in and both treatment periods separately and overall. Adverse events will be tabulated by System Organ Class and Preferred Term based on MedDRA version 22.0. Adverse events will also be summarized by seriousness, severity, and relationship to study procedures and the investigational device. Except where indicated, a subject reporting the same adverse event more than once will be counted once when calculating the number and percent of subjects with that particular event.

Adverse events leading to death or to discontinuation from the study will be listed separately. A listing of all adverse events will be provided.

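### The Safety analysis set leaves out anyone who used the investigational Control-IQ 1.5 pump but did not reach Visit 6, so their adverse events drop out of the run-in and overall tables and the primary event counts

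*Combined protocol and SAP*

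**What the plan says.** Section 8.5 (Analysis Datasets) gives the definition: "Safety analysis set: All participants who initiate the Treatment Period and use the study device at least one time (including training". Both conditions must be met, and no other safety population is defined.

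The run-in and the Treatment Period are separate phases throughout the document. On entry to the second, section 3.3 says: "After participants complete the run-in, they will return for the Control-IQ 2.0 training visit". On the device used in the first, section 4.1.1 says: "For the run in period, participants will use a study provided Tandem t:slim X2 with Control-IQ 1.5 technology (Investigational Device". Adverse events are reviewed during the run-in, at the Visit 3 to 5 contacts (section 3.2).

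The analysis sections then apply the set to both phases:

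- Section 8.6.1: safety events "will be based on Safety analysis set, and tabulated for each primary endpoint as the number of events per participant". The proportions with events in each treatment period "will be compared with the run-in period as well as with the T1D Exchange frequency".
- Section 8.6.2: "Safety summaries will be based on Safety analysis set". Adverse events are to be "summarized by study period for run-in and both treatment periods separately and overall".

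Primary endpoints 3 and 4 in section 8.4 (UADEs and other serious device-related adverse events) are not limited to the Treatment Period. Endpoints 1 and 2 (severe hypoglycemia and diabetic ketoacidosis, DKA) are worded as occurring during the study.

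**The concern.** The stated purpose of the study is safety, and participants wear an investigational pump from Visit 2. Under section 8.5, someone who stops between Visit 2 and Visit 6 contributes no events and no person-time to any table built on the Safety analysis set, including the column headed run-in.

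The exclusion can depend on the event itself. Section 6.6.1 ends device use when the investigator judges continuation unsafe, and that criterion is not limited to the Treatment Period. Section 3.8 says a participant who stops the device before the final visit is then dropped from the study. A malfunction that caused, or could have caused, severe hypoglycemia or DKA leads to suspension of the device pending approvals (section 6.6.1). Section 3.1.1 says participants may be asked to leave if Control-IQ must be stopped for more than a few days. These last two provisions do not make withdrawal automatic, but a run-in event serious enough to be a UADE is the kind that could keep someone out of the set used to count UADEs.

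At stake is whether the tabulated primary endpoints of a safety study include every event on an investigational pump. A second issue is that the run-in side of the section 8.6.1 comparison is conditional on reaching Visit 6, and the plan does not say so.

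**Working it through.** **Step 1: who is in the set.** Take a participant who starts Control-IQ 1.5 at Visit 2, has a reportable event on day 7 and leaves.

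- Used a study device at least once: yes.
- Initiated the Treatment Period: no, because Control-IQ 2.0 starts at Visit 6.
- In the Safety analysis set: no, because both conditions are required.

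**Step 2: where the event appears.**

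- Primary endpoint tabulation (8.6.1): absent.
- Run-in and overall adverse event summaries (8.6.2): absent.
- Listing of all adverse events, and separate listing of those leading to discontinuation (8.6.2): present.
- Number not entering the Treatment Period, with reasons (8.8): person counted.
- Expedited reports (6.4): present if the event qualifies.
- Device issue tabulation (8.11): undetermined, because no set is named.

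**Step 3: how many people.** The documents give no run-in dropout figure. Up to 100 sign consent and at least 72 are to complete (30 + 30 + 12 = 72). The difference of 100 - 72 = 28 also includes screen failures and Treatment Period dropouts, so at these planning numbers the number affected lies between 0 and 28.

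**Step 4: size, as an illustration.** The plan states no figure to reproduce. Assumptions: 72 participants in the present set, all with three full 14-day periods; one event, in a run-in-only user; 7 days of use per leaver. Section 8.6.1 names no interval method, so exact Poisson limits are used.

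Person-years (PY) in the present set:

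- run-in: 72 × 14 / 365.25 = 2.760
- overall: 72 × 42 / 365.25 = 8.279

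Each leaver adds 7 / 365.25 = 0.019 PY. Rate per 100 PY = 100 × events / PY. The 95% limits for x events in T PY are 100 × χ²(0.025; 2x) / 2T, taken as 0 when x = 0, and 100 × χ²(0.975; 2x + 2) / 2T.

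| | Present set, 0 events | Any-pump set, 1 event, 1 leaver | Any-pump set, 1 event, 10 leavers |
|---|---|---|---|
| Run-in PY | 2.760 | 2.779 | 2.951 |
| Run-in rate (95% CI) | 0 (0 to 133.7) | 36.0 (0.9 to 200.5) | 33.9 (0.9 to 188.8) |
| Overall PY | 8.279 | 8.298 | 8.471 |
| Overall rate (95% CI) | 0 (0 to 44.6) | 12.1 (0.3 to 67.1) | 11.8 (0.3 to 65.8) |
| Participants with an event, run-in | 0/72 = 0% | 1/73 = 1.4% | 1/82 = 1.2% |

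**Step 5: sensitivity.**

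- With 1 to 10 leavers and 1 to 14 days of use each, the run-in rate lies between 31.8 and 36.2 and the overall rate between 11.5 and 12.1.
- With 28 leavers who each used the pump for the full run-in, the run-in rate is 26.1 (0.7 to 145.4).
- The bias can also go the other way. With one run-in event inside the present set and 10 event-free leavers at 7 days, the present rate is 100 / 2.760 = 36.2, against 100 / 2.951 = 33.9 with the leavers counted.
- With no run-in-only users, nothing changes.

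**The case against.** The best defence is that the set suits the question. The objective is the safety of Control-IQ 2.0, version 1.5 is the designated comparator (section 8.2), the stopping rule in section 6.6.2 counts events in people who have started 2.0, and the baseline table in section 8.9 uses the same cohort. Comparing periods within the same people is valid. All of this stands for the treatment columns and the paired comparisons. It does not justify a run-in or overall column, or a study-wide UADE count, on that set.

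Second, other text points towards inclusion. Section 7.7 says withdrawn participants' data are used up to withdrawal, and section 8.6.2 speaks of all adverse events reported over the course of the study. But the sentence in 8.6.2 follows directly after the one tying the summaries to the Safety analysis set, and section 7.7 is a general statement that does not alter the definition in 8.5. These provisions show an inconsistency and do not remove the exclusion.

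Third, nothing is hidden: "Adverse events leading to death or to discontinuation from the study will be listed separately", a listing of all events is promised, and UADEs go to the IRBs and FDA. That is correct and limits the harm, but a listing does not correct an endpoint count.

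Fourth, the route is narrow. The automatic discontinuation rules for severe hypoglycemia and DKA in section 6.6.1 apply only in the treatment period, so a participant with such an event in the run-in may continue to Visit 6 and be counted. The intervals in the illustration overlap almost entirely, and section 8.2 plans no formal inference. Both points stand and are why the priority is not higher.

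**Conclusion.** The concern holds. As written, section 8.5 excludes run-in-only users of an investigational pump from the run-in and overall safety tables and from the primary endpoint tabulations. Endpoints 3 and 4 could be undercounted. A severe hypoglycemia or DKA event in such a person would likewise be missing from the tabulation of endpoints 1 and 2.

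The practical effect is a count that could read 0 when the study had 1. The shift in rates shown above is secondary, very imprecise, and rests on assumed numbers of events, leavers and days of use, none of which the documents give. The Treatment Period columns and their comparison with the T1D Exchange registry do not change. Comparing run-in with treatment among those who reached Visit 6 is defensible once it is labelled as such. The number of people affected may be zero, so this is a low-to-moderate priority.

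**What to change.** In section 8.5:

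1. Define the Safety analysis set as all participants who use either study pump (Control-IQ 1.5 or 2.0) at least once.
2. Keep the present set under its own name, for example the Control-IQ 2.0-treated set, for the treatment columns and the within-participant comparisons.

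In sections 8.6.1, 8.6.2 and 8.11:

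3. Report the run-in column, the overall adverse event summaries and the UADE and device-related event counts on the wider set, with actual person-time.
4. State that the run-in side of the paired comparisons is conditional on reaching Visit 6.
5. Name the set used for the device issue tabulation.
6. Bring the statements in sections 7.7 and 8.6.2 into line with the revised definition.

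The cost is one reworded definition, one extra named set and stated denominators in the table shells. No new data are needed, because adverse events are already reviewed at the run-in contacts. The CGM and meal-challenge sets keep the same members, since each also requires 24 hours of Treatment Period CGM data. The one drawback is that the run-in column and the paired comparison will have different denominators, which a footnote can explain.

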516 517 518	 Full bolus for the given carbohydrates and calculated correction, given 45 minutes after starting the meal, based on calculated bolus dose using the bolus calculator (with full amount of carbohydrates entered).
519 520 521	• Full bolus for the given carbohydrates and calculated correction, given 45 minutes after starting the meal, based on calculated bolus dose using the bolus calculator (with full amount of carbohydrates entered) AND enabling the late bolus feature to 45 minutes later.
522	For each meal challenge, participants will:
523 524	1. Be in a fasting state for two hours prior to consuming the last meal of the day, with the last manual insulin bolus more than two hours prior to the meal.

- 525 2. For participants age 6+, only begin the meal challenge if CGM glucose is between 70 mg/dL and 200 mg/dL, and CGM trend arrow is not down.
- For participants age 2-5, only begin the meal challenge if CGM glucose is between 70 mg/dL and 250 mg/dL, and CGM trend arrow is not down.
- 529 Subjects with hyperglycemia > 200mg/dL will reschedule their challenge for another time. If < 530 To mg/dL, carbohydrate treatment can be given, after which the meal challenge can continue.
 - 3. Pediatric participants age 2-5 should have a meal with at least 20 grams of carbohydrates. Participants age 6-13 should have a meal with at least 35 grams of carbohydrates. All other participants should have at least 50 grams of carbohydrates for the study meal challenges. *Each participant should use the same meal for all of their meal challenges in the study. Participants will be encouraged to use the same frozen entrée of their choice for consistency.*
 - 4. Do their best to complete the meal within 30 minutes of starting to eat.
 - 5. Write down the start and end time of eating the meal, as well as the meal content (to include amount of carbohydrate, protein and fat) on the study provided logbook.
 - 6. Bolus for the meal 45 minutes after starting to eat, entering the full carbohydrate amount and using the recommended dose from the bolus calculator. For one of the two challenges during a single treatment period, use the bolus calculator but do not change the bolus time. For the other challenge during the same treatment period, use the bolus calculator but change the bolus time to 45 minutes late.

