8.6.3 Analysis of CGM Endpoints

CGM metrics will be assessed in CGM analysis set, and computed for the Run-In and both Treatment Periods separately. CGM metrics will be computed per subject over 24 hours, during daytime (6am-11:59pm), and during nighttime (12am-5:59am), as well as by age cohort (adults/adolescents, children 6 – 13, and preschool), baseline HbA1c cohort (HbA1c at baseline of ≥ 7.5%,yes/no), and target activity use as specified by the device (standard target, lower target, sleep activity, and exercise activity). The main statistical comparison will be made between the three 2-week periods (Run In, Treatment

The main statistical comparison will be made between the three 2-week periods (Run In, Treatment Period at standard target, Treatment Period at lower target). The comparison will be pairwise – Run-in vs standard targe, Ru-in vs lower target, and standard vs lower target. The percent time in glycemic ranges will be calculated as the number of measurements in the specified range divided by the total number of measurements for which it can be determined whether or not the measurement was in specified range.

The "Low" and "High" CGM readings will be included in all analyses. Percent time will be compared using a paired t-test assuming sufficient normality assumptions hold, otherwise an appropriate non-parametric method will be utilized.

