8.6.4 Analysis of Late Bolus Meal Challenges

All analyses in section 8.6.4 will be conducted in the late bolus meal challenge analysis set. Data included in these analyses will be restricted to data during the meal challenge window (start of meal through 5 hours from meal imitation [3 hours for age 2-5]). The subgroups assessed will be the same as sections 8.6.1 − 8.6.3 (age cohort, baseline HbA1c cohort (HbA1c at baseline of ≥ 7.5%. yes/no), etc.)

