8.6.4.1 Late Bolus Meal Challenge Safety and CGM Subgroup Analysis

Two challenges are expected per subjects per treatment period for a total of four challenges, therefore agreement of outcomes will need to be assessed. For continuous outcomes, two sets of Pearson's correlation coefficients will be calculated to measure concordance: one restricted to each treatment period (higher range target and lower range target), and a single coefficient for all four challenges. For categorical outcomes, a Cohen's kappa statistic for agreement or a similarly appropriate statistic will be calculated and presented to describe agreement/dependence of outcomes by individual subjects. Results will be compared by treatment period and across treatment periods.

The analyses described in sections 8.6.1, 8.6.2, and 8.6.3 will be repeated for subjects included in the late bolus meal challenge set. For the CGM outcomes, the mean of the CGM metrics for the two late meal

bolus challenges within study period will be used to account for within-subject non-independence (i.e. one data value per subject per study period).

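### The meal-challenge set applies a flat 3-hour CGM minimum to one challenge only, and the analysis then averages normal-bolus and late-bolus challenges together

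*Combined protocol and SAP*

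**What the plan says.** **Entry to the set (section 8.5).** A participant must belong to the Safety set, have 24 hours of CGM data in the Treatment Period, and be someone "who has at least 3 hours of CGM data for at least one meal" challenge. The 3 hours are the same at every age, and one challenge is enough.

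**Window and scope (section 8.6.4).** Only data from "start of meal through 5 hours from meal imitation [3 hours for age 2-5" are analysed. Every analysis under 8.6.4 uses this set: CGM metrics, adverse events, time to intervention and number of interventions.

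**Combination (section 8.6.4.1).** "Two challenges are expected per subjects per treatment period for a total of four challenges". For CGM outcomes, the mean of the two "bolus challenges within study period will be used to account for within-subject non-independence", giving one value per participant per period.

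**What the two challenges are (section 5.1.1).** In both, the full bolus is given 45 minutes after the meal starts. "For one of the two challenges during a single treatment period, use the bolus calculator but do not change the bolus time"; for the other, the bolus time is changed to 45 minutes late, which is the late bolus feature.

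**Denominator and missing data.** Percent time is "the number of measurements in the specified range divided by the total number of measurements" that can be classified (section 8.6.3). Section 8.15 uses available data without imputation.

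**The question asked (section 8.4).** Secondary endpoint 7 compares late bolus feature use with normal bolus in the challenges, for the CGM metrics and adverse events.

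**The concern.** There are two linked gaps.

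First, the window is shortened for ages 2-5 but the data minimum is not. The CGM-set definition just before it in section 8.5 does carry the 3-hour bracket for the youngest. No reason is given for leaving preschoolers no slack while others may miss two fifths of the window. Because the set also governs adverse-event and intervention summaries within the challenges, a CGM gap can remove a child from analyses that do not need complete CGM data.

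Second, the minimum is checked on one challenge and never again. A participant's other challenges enter the period mean however little was recorded, and nothing says what to do when only one challenge in a period has data. The two challenges being averaged are also the two conditions that endpoint 7 sets against each other. At stake is whether the meal-challenge analysis can answer its own question, and whether its comparison of targets is like with like.

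**Working it through.** The documents state no coverage percentage, CGM loss rate or power for this analysis, so there is no figure of the plan's own to reproduce.

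**1. Share of the window required** (minimum from 8.5, window from 8.6.4)

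- Age 6 and over: 3 h / 5 h = 60%, so 40% may be missing.
- Ages 2-5: 3 h / 3 h = 100%, so nothing may be missing.

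**2. How many preschoolers could be excluded.** Let p be the chance that one 3-hour window is complete. It is not in the documents and is taken over a range, with challenges assumed independent. With k challenges done, the chance that none is complete is (1 − p)^k, and the expected number excluded from 12 (the minimum number of completers, section 8.3) is 12 × (1 − p)^k.

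| p | four done: 12 × (1 − p)^4 | two done: 12 × (1 − p)^2 |
|---|---|---|
| 0.9 | 0.001 | 0.12 |
| 0.7 | 0.10 | 1.08 |
| 0.5 | 0.75 | 3.0 |
| 0.3 | 2.9 | 5.9 |

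Exclusion is rare unless gaps are frequent or few challenges are done.

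**3. Unequal coverage, equal weight.** Assumed example on a 5-minute grid: one full 5-hour challenge (60 readings) at 60% in range, and one with 15 minutes of data (3 readings).

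- Fragment at 0% in range: simple mean (60 + 0)/2 = 30%; weighted by readings (60 × 0.60 + 3 × 0)/63 = 57%.
- Fragment at 100% in range: simple mean (60 + 100)/2 = 80%; weighted by readings (60 × 0.60 + 3 × 1)/63 = 62%.

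**4. One usable challenge in a period.** Let N and L be a participant's values with normal and late bolus, and δ the difference between targets, assumed additive.

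- Both challenges usable at both targets: the difference in period means is δ.
- Both usable at one target, only normal bolus at the other: (N + δ) − (N + L)/2 = δ + (N − L)/2. Half the bolus effect enters the target comparison.
- Only normal bolus at one target and only late bolus at the other: δ + (N − L). The whole bolus effect enters.

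**5. Complete data.** The period value is (N + L)/2. It depends only on the sum, so L − N, which endpoint 7 asks for, cannot be recovered from it. The Pearson and kappa statistics in 8.6.4.1 describe agreement between challenges, not the difference between them.

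**6. A common 60% share.** For ages 2-5 it is 0.6 × 3 h = 1.8 h, or 22 of 36 readings on a 5-minute grid. With 5% or 10% of readings lost independently (assumed), a window meets this with probability above 0.999. If recording is continuous from meal start, 108 minutes of data end 108 − 45 = 63 minutes after the bolus. The corresponding figure at age 6 and over is 180 − 45 = 135 minutes.

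**The case against.** A reader might infer that the entry rule will cost the study much of its preschool cohort. The documents do not support that. They give no CGM loss rate, and one complete window of four is enough. A large loss appears only under a particular model: 5-minute readings, 5% of them lost independently, and a strict 36-of-36 count give 12 × (1 − 0.95^36)^4 = about 6 of 12. Changing either assumption removes most of it:

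- The same 5% loss in gaps averaging 30 minutes (two-state model, assumed) gives a complete window with probability 0.95 × (1 − 0.0088)^35 = 0.70, and an expected loss of about 0.1 of 12. With 60-minute gaps the probability is 0.81 and the loss about 0.01.
- The plan does not say how hours are counted. Minutes 0 to 180 inclusive hold 37 readings. If 36 of them count as 3 hours, one may be missing, and independent 5% loss then excludes about 10% of children.

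Loss concentrated in particular children would push the other way.

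The plan also has safeguards. Entry requires 11 of the prior 14 days of CGM use. A working CGM is needed before each challenge, a parent stays and watches the readings, and staff receive real-time alerts for all 2-5 year olds during Control-IQ 2.0 use. Nor is it true that every challenge rule is scaled by age: the bolus delay, the fast before the meal and the spacing of challenges are common to all. An equal absolute minimum is defensible in principle. An excluded child's adverse events would still appear in the overall safety tables of 8.6.1 and 8.6.2. All of this is secondary analysis in a study without formal hypotheses.

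These arguments limit the size of the exclusion problem. They do not touch the missing minimum for each challenge or the averaging of two different conditions. An analyst might compare late with normal bolus anyway because 8.4 names that contrast, but 8.6.4.1 describes a different summary for the CGM outcomes.

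**Conclusion.** The point stands in three parts.

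- **Entry rule:** 100% against 60% of the window is plain arithmetic from the text and rests on no assumption. Its effect is probably small, about 0.1 of 12 preschoolers or fewer if windows are complete at least 70% of the time and all four challenges are done. It becomes material, at 3 of 12, if completeness is near 50% and only two are done. These figures assume independent challenges and a value of p that the documents do not give.
- **No minimum for each challenge:** a fragment can carry half the weight of a period value, and a period with one usable challenge can put half or all of the bolus effect into the target comparison. How often this will happen is unknown.
- **Averaging across bolus types:** this needs no missing data. As written, the CGM analysis in 8.6.4.1 removes the contrast of secondary endpoint 7. It is the most important of the three.

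The primary endpoints are not affected. This should be corrected before analysis because the remedy uses data already planned for collection.

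**What to change.** 1. In 8.5, define a usable challenge as one with CGM data for a common share of the age-specific window, for example 60% (the share already implied for age 6 and over): 3 h of 5 h, or 1.8 h of 3 h at ages 2-5. Apply it to each challenge and state how hours of data are counted.
2. Use this minimum for CGM metrics only. Adverse-event and intervention summaries should include every Safety-set participant who performed a challenge.
3. In 8.6.4.1, replace the period mean with an analysis of each usable challenge, with bolus type and target as terms and participant as the repeated unit. This handles the within-participant dependence that the averaging was meant to address. A simpler alternative compares late with normal bolus within participant, in periods where both challenges are usable.
4. Report coverage for each challenge by age cohort and bolus type.

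**Cost.** A few sentences in two sections, with no new data and no change to procedures. A few sparse challenges will drop from the CGM metrics at age 6 and over. A 60% share of 3 hours can leave part of a preschooler's post-bolus period unobserved, which is why coverage should be reported.
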